Appendix

Appendix A

Levels of Evidence Synthesis Table

Level of evidence for intervention questions	1	2	3	4	5
I-Systematic Review/Meta-analysis of randomized controlled trials					
II-Single randomized controlled trials					
III-Quasi-experimental studies/non-randomized controlled trials				X	
IV-Cohort or case-control studies	X		X		X
V-Systematic review/meta-synthesis of qualitative studies					

VI-Single qualitative or descriptive studies/evidence implementation and quality improvement projects		X			
VII-Expert Opinion					

Studies in alpha-order: Brosey, Grillo, Kuwaiti, Olrich, Reimer

Appendix B

PICOT Question:

For adult patients in the hospital (P), how does hourly rounding (I) compared to no hourly rounding (C), affect incidence of falls (O) during the patient's hospital stay (T).

Evidence Synthesis Table

Studies	Design	Sample	Intervention	Outcome
A	Systematic literature review	Sample Size varied for each of the 14 studies evaluated	Rounding	
Brosey & March (2014) – FR decreased from 7.02 to 3.18/1,000 PD
 
Ciccu-Moore et al (2014) – FR decreased 39% during study period
 
Dupree et al (2014) – FR decreased from 4.001 to 2.613/1,000 PD
 
Fisher et al (2014) – FR decreased from 5.42 to 3.94/1,000 PD
 
Ford (2010) – No falls reported during the study
 
Kolin et al (2010)- FR decreased from 361 to 214
 
Krepper et al (2012) – FR on control and experimental units were similar
 
Kessler et al (2012) – FR decreased from 5.46 to 2.19/1,000 PD
 
Meade et al (2006) – 25 falls in four weeks prior to intervention, 12 falls during intervention period
 
Olrich et al (2011) – FR decreased from 3.37 to 2.6/1,000 PD, 23% decrease in falls
 
Saleh et al (2011). FR decreased from 25 falls to 4
 
Sherrod et al (2012) – FR slightly increased from 4.3 to 4.5

				Tucker et al (2012) – FR 4.5, 1.6, and 3.2, decreasing at first then increasing Woodward (2009)- FR decreased
B	Descriptive Study – pilot project	N=60	IR	-FR decreased 44% from 442 per 1,000 PD to 247 per 1,000 PD from the pre-implementation to post implementation time L/D P -There was an 81% reduction in replacement costs from pre-implementation and post-implementation time
C	Descriptive Study – clinical practice improvement project	N=245	FPP	-With implementation of the FPP, there was a 54% reduction in FR from 2.51 per 1,000 PD for 2014, to 1.15 FR per 1,000 PD for the last half of 2016 and the first half of 2017. -There was a 72% reduction in SU after the implementation of the FPP, that resulted in \$84,000 in savings.
D	Explanatory cross-sectional Study	N=2,170 RN surveys	RNV– including BS, NL, AL, MN,	BS – 4.10 EM (0.69 SD) NL- 4.03 EM (0.68 SD) AL – 4.06 EM (0.69 SD) MN – 3.88 EM (0.78 SD) PP – 4.07 EM (0.69 SD)
E	Retrospective Study- medical record review	N=140	FPP (including bed/chair alarms, hourly rounding, patient education)	FR decreased 0.6 falls per 1,000 PD
F	Descriptive Study – Virtual breakthrough series improvement project	PFH N=19 teams SE N=15 teams	PFH SE IR	FR before interventions 28.5, FR post intervention 27.5 (p=0.136) = not significant FRI= before interventions 6.6 (p=0.009), IJR post intervention 6.5 (p=0.005)

		IR N=13 teams		
--	--	------------------	--	--

Legend: A = Hicks, D., 2015, B = Jenko, M. & Panjwani, Y., & Buck, H., 2019, C = Spano-Szekely, L., Winkler, A., Waters, C., Dealmeida, S., Brandt, K., Williamson, M., Blum, C., Gasper, L., & Wright, F., 2019, D = Tzeng, H. & Yin, C., 2017, E = Wilbert, W. 2013, F = Zubkoff, L., Neily, J., Delanko, V., Young-Xu, Y., Boar, S., Bulat, T., & Mills, P. D., 2019, R=rounding, IR= intentional rounding, HR= hourly rounding, FR= fall rate, PD= patient days, L/D P= lost/damaged possessions, FPP=fall prevention program, SU=sitter usage, RNV= RN vigilance, BS=bathroom support, EM= effectiveness mean, SD=standard deviation, BS=bathroom support, NL=night light, AL=adjust lighting, MN=minimize noise, PP=personal possessions, PFH=post fall huddle, SE=staff education, FRI=fall related injury

Outcomes Table: Effect of hourly rounding on fall rate

	A*	B*	C*	D*	E*	F
FR	↓↓↓↓↓↓↓-↓↓↓↓↑-↓	↓	↓	↓	↓	-
L/D P		↓				
SU			↓			
FRI						↓

Legend: A = Hicks, D., 2015, B = Jenko, M. & Panjwani, Y., & Buck, H., 2019, C = Spano-Szekely, L., Winkler, A., Waters, C., Dealmeida, S., Brandt, K., Williamson, M., Blum, C., Gasper, L., & Wright, F., 2019, D = Tzeng, H. & Yin, C., 2017, E = Wilbert, W. 2013, F = Zubkoff, L., Neily, J., Delanko, V., Young-Xu, Y., Boar, S., Bulat, T., & Mills, P. D., 2019, R=rounding, IR= intentional rounding, HR=hourly rounding, FR=fall rate, PD= patient days, L/D P= lost/damaged possessions, FPP=fall prevention program, SU=sitter usage RNV= RN vigilance, BS=bathroom support, EM= effectiveness mean, SD=standard deviation, BS=bathroom support, NL=night light, AL=adjust lighting, MN=minimize noise, PP=personal possessions, PFH=post fall huddle, SE=staff education, FRI=fall related injury

* = statistically significant findings

Recommendations

Based on results from study findings, I recommend that hourly rounding be implemented along with other fall prevention interventions to reduce potential for falls and/or fall related injury within the acute care setting. Falls have devastating and lasting repercussions on the patient, the patient's family, healthcare staff, as well as the facility. In my opinion, any intervention that has potential to decrease a fall and injuries related to falls, must be implemented. My PICOT question and article studies investigated the effects that an hourly rounding program can have on decreasing the fall rate. Most of the articles I selected to appraise showed a decrease in fall rate. Article A, (Hicks, 2015), was a literature review that summarized fourteen study findings related to hourly rounding used as a fall prevention intervention. In all fourteen studies investigated in this article, only one showed an increase in the fall rate after hourly rounding, and two showed no change. This review highlights eleven studies that found hourly rounding to have a decreasing effect on falls.

I also feel that hourly rounding be one component of a fall prevention program, but that other tools and interventions be applied. Through my research, I discovered that many facilities use an individualized fall assessment tool that helps tailor an assessment based on the patient's risks and needs. I believe that this assessment tool, prescribed interventions based on the assessment, and a systematic hourly rounding process, will help to reduce the incidence of falls.

References

- Hicks, D. (2015). Can rounding reduce patient falls in acute care? An integrative review. *Medsurg Nursing, 24*(1), 51-55.
- Tzeng, H. & Yin, C. (2017). A multihospital survey on effective interventions to prevent hospital falls in adults. *Nursing Economics, 35*(6). 304-313.

Appendix C

Rounding Survey

Patient's Name: _____
Last First

Overall, how would you rate your interaction with our staff?

Worst Best

1. Patients are to be rounded on, or checked on, every hour during the day and every two hours at night. Do you feel that this happened during you stay at our facility?

YES

NO

2. Did staff ask you about your pain level during these rounds?

YES

NO

3. Did staff ask you about your bathroom needs during these rounds?

YES

NO

4. Did staff make sure that your belongings were within your reach during these rounds?

YES

NO

5. Did staff check to see if the environment was comfortable for you during these rounds? (Room temperature, lighting, noise level)

YES

NO

6. Did staff look for trip hazards and make sure the call light was within your reach during these rounds?

YES

NO

Thank you for taking the time to complete this survey.

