After staff education about purposeful, hourly rounds and all expectations connected to the process, the intervention will be implemented over a twelve-week time. The rounds are to be completed hourly from 0700 to 2200 and every two hours from 2300 to 0600. During the rounds, staff are to assess the patient's pain, bathroom needs, proximity to possessions, body positioning, and peacefulness of their environment. Staff will also assess and monitor for trip hazards, closeness of the call light, and use of bed rails/bed alarm. These rounds will be documented, after completion, in the patient's electronic medical record. Patients will be given a survey to fill out on the day of discharge, about the rounding experiences.

Study Stage – 1 week

During this stage, the fall rate from twelve weeks prior to implementation of the hourly rounding process will be compared to the fall rate for the twelve-week implementation time. Any fall that occurs during this time must be analyzed using root cause analysis to determine if it was accidental or intentional. An audit of video monitoring and chart audits of hourly rounding

documentation will be used to evaluate if hourly rounding had been completed, as expected. Feedback scores from patient surveys will be compiled and evaluated.

Act Stage- 1 week

After evidence of the effect that hourly rounding has on fall reduction, this process will be adopted as policy. New rounding policy and procedure will be adopted, and the process will be extended to and shared with other units within the facility.

Timetable/Flowchart

PLAN Phase – 2 weeks - Project evidence shared with stakeholders; project education completed

DO Phase – 12 weeks – Hourly rounding implemented, patient surveys on rounding sent to patients to be completed and returned

STUDY Phase – 1 week – Fall rates for pre and post implementation period is compared, video monitoring completed, chart audits of rounding documentation

ACT Phase – 1 week- Data shared with administration, new rounding policy adopted, rounding procedure policy expanded to other units

Data Collection Methods

The center of quality improvement is the planned effort to test a change decipher its result on a desired outcome. One widely utilized method for testing and learning about a change and its desired outcome is the PDSA or, plan, do, study, and act, method, (Melnik & Fineout-Overholt, 2019). This method will be used to implement my change project. After the “DO” phase, the

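### The Appendix C rounding survey cannot measure adherence to all eight required rounding elements and may overstate it

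*Protocol*

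**What the plan says.** The Do Stage of the protocol's Implementation section sets the content of each round in two sentences. In the first, "staff are to assess the patient's pain, bathroom needs, proximity to possessions, body positioning, and peacefulness of their environment". The second adds: "Staff will also assess and monitor for trip hazards, closeness of the call light, and use of bed rails/bed alarm". Counting bed rails/bed alarm as one element, as the protocol lists it, that makes eight.

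The Executive Summary names patient surveys, with fall-rate comparisons, video monitoring and chart audits, as what will prove implementation. Data Collection Methods says the survey asks about the frequency and the content of rounds.

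The form in Appendix C asks for the patient's name and an overall rating of the interaction with staff, followed by six numbered yes/no items. Item 1 opens with "Patients are to be rounded on, or checked on, every hour during the day and every two hours at night" and then asks "Do you feel that this happened during you stay at our facility". Items 2 to 5 cover pain, bathroom needs, belongings and environment. Item 6 reads "Did staff look for trip hazards and make sure the call light was within your reach during these rounds".

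Delivery is described in two ways. The Do Stage says "Patients will be given a survey to fill out on the day of discharge, about the rounding experiences". The Timetable/Flowchart has "patient surveys on rounding sent to patients to be completed and returned".

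**The concern.** The survey is the only planned source on the content of rounds that does not come from staff. By Data Collection Methods, video shows staff entering and leaving rooms, and chart audits review documentation that staff enter themselves. Neither tells an outside observer whether the call light was placed within reach or the bed alarm checked.

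The form falls short of this use in three ways. Item 1 supplies the expected answer before asking for it, and its single yes/no does not show whether a no refers to the day or the night schedule. Item 6 does not separate its two elements. Two required elements are not asked about at all. The gaps matter for the intervention: the Rationale names the call light and the bed alarm among the simple tasks expected to have a large effect on falls, yet the form merges the call light with another element and leaves the alarm out.

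The two delivery descriptions add a further problem. A form completed at discharge and a form sent out for return can be expected to have different non-response, and the protocol does not settle which applies.

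At stake is what the project can claim about delivery of the revised process when administration decides whether to adopt and extend it.

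**Working it through.** The plan states no adherence figure, so there is nothing to reproduce. The check matches the Do Stage elements to the Appendix C items.

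| Required element (Do Stage) | Survey item (Appendix C) |
|---|---|
| Pain | 2 |
| Bathroom needs | 3 |
| Possessions | 4 |
| Environment | 5 |
| Trip hazards | 6, shared |
| Call light | 6, shared |
| Body positioning | none |
| Bed rails/bed alarm | none |

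Own item 4 + shared 2 + none 2 = 8. The survey touches 6 of 8 elements and isolates 4.

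**Load on item 1.** Hourly rounds from 0700 to 2200 inclusive give 16. Two-hourly rounds from 2300 to 0600 give 4 (2300, 0100, 0300, 0500). One yes/no therefore covers about 16 + 4 = 20 rounds per day, under two schedules, over the whole stay.

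**Direction of bias.** The documents give no adherence rates. The figures below rest on assumed rates and independence, and show direction only.

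- *Omitted elements.* If each element is done with probability p, all eight are done with probability p^8 and the six surveyed with p^6. At p = 0.80: 0.80^8 = 0.17 against 0.80^6 = 0.26. At p = 0.90: 0.43 against 0.53. Reading the six as the full set overstates adherence. Reading them as six elements does not.
- *Item 6.* At p = 0.80 for each part, yes has probability 0.80 × 0.80 = 0.64 if the patient requires both, and 1 − 0.20^2 = 0.96 if either is enough, against 0.80 for each element alone. The error can go either way.
- *Items 2 to 6.* Each asks whether something was done during the rounds, without saying how often. If one remembered instance is enough for a yes and an element is done at a fraction f of 20 rounds, a one-day patient can answer yes with probability 1 − (1 − f)^20. For f = 0.05 this is 0.64, for f = 0.10 it is 0.88, and for f = 0.20 it is 0.99. This pushes upward.
- *Item 1.* The lead-in pushes upward. Two things push the other way. Patients asleep may miss the night rounds, which are 4 of 20. A patient who answers literally says no after one missed round: with each round completed at 0.90, all 20 are completed with probability 0.90^20 = 0.12.

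**The case against.** The strongest case on the other side is that the survey is a minor process measure. It does not enter the comparison of falls per 1,000 patient days, and the Act Stage ties adoption to evidence of fall reduction, not to survey scores. Frequency, the subject of item 1, is also checked by video and chart audit. The Executive Summary lists four sources together and does not rest implementation on the survey alone. Stakeholders gives administration the task of creating patient surveys, and the body text does not cite Appendix C, so the form may not be final. All of this stands and limits the weight of the point. It does not remove it: Appendix C is the form the protocol provides, and neither video nor charts give a non-staff view of content. If the form is a draft, correcting it is cheaper still.

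A reader might infer more than the documents support:

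- *That the survey will overstate adherence.* The joined item has no fixed direction, omitted items leave elements unmeasured rather than inflated, and sleeping patients may under-report. The protocol defines no full-set score; it says only that survey scores will be compiled and evaluated.
- *That the survey cannot show which element failed.* Items 2 to 5 isolate four elements. Among those surveyed, only the pair in item 6 cannot be separated.
- *That patients answer under pressure because they are still in the unit's care.* This holds only for day-of-discharge completion, and the delivery mode is unsettled. The "Patient's Name" field could discourage criticism under either mode, but the documents do not show how much.
- *That the lack of a baseline survey is an error.* No before-and-after survey comparison is planned, and an adherence check does not require one.

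**Conclusion.** The point holds in a limited form. As printed, the survey cannot measure adherence to all required elements: two of eight have no item, two share one answer, and the frequency item is led and merges day with night. It may overstate adherence. The lead-in, and yes/no items that a single instance can satisfy, make an upward bias more likely than not, but this is a judgement about how patients answer, not a result from the documents. The size of the bias cannot be derived from them, and the probabilities in the working depend on assumed adherence rates and independence. The two delivery descriptions conflict and must be reconciled. The fall-rate comparison is untouched. The edits are worth making because the Executive Summary treats the survey as proof of implementation and they cost almost nothing.

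**What to change.** Edit the Appendix C form and the two delivery descriptions:

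1. Remove the statement of the standard from item 1. Replace the item with two questions, one on how often staff checked during the day and one on the night.
2. Split item 6 into one item on trip hazards and one on the call light.
3. Add one item on body positioning and one on bed rails/bed alarm.
4. Choose one delivery mode, state it identically in the Do Stage and the Timetable/Flowchart, and report the response rate.

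The numbered items rise from 6 to 10: one more from item 1, one more from item 6, and two new. The cost is four extra questions on a one-page form.

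Removing the name and surveying before implementation are optional. The first would give up any link from answers to a named chart, though the protocol describes no such link. The second would help separate the revised process from existing rounding, but requires printing and distributing forms earlier.
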